### 5.3.2 Dose Modifications/Delays for Cetuximab (Rash)

Severe Acneiform Rash	Cetuximab Dosing	Outcome	Dose modification
1 st occurrence	Delay infusion 1 to 2 weeks	Improvement	Continue 250 mg/m 
		No improvement	Discontinue Cetuximab
2 nd occurrence	Delay infusion 1 to 2 weeks	Improvement	Reduce to 200 mg/m 
		No improvement	Discontinue Cetuximab
3 rd occurrence	Delay infusion 1 to 2 weeks	Improvement	Reduce to 150 mg/m 
		No improvement	Discontinue Cetuximab
4 th occurrence		Discontinue Cetuximab	

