**Management guidelines for skin toxicity (grade  $\geq 2$ ) are provided in Appendix 12.1**

### **5.5 Prohibited Medications/Treatments**

There are no reported drug-drug interactions with cetuximab. However, palbociclib, is primarily metabolized by CYP3A and sulfotransferase enzyme (SULT2A1). In vivo, palbociclib is a time-dependent inhibitor of CYP3A. The patient handout in Appendix 12.2 should be provided to patients to inform them of drugs to avoid taking while they are receiving study medications.

Prohibit use of strong CYP3A inhibitors ie, clarithromycin, indinavir, itraconazole, ketoconazole, lopinavir/ritonavir, nefazodone, nelfinavir, posaconazole, ritonavir, saquinavir, telaprevir, telithromycin, and voriconazole. Avoid grapefruits and grapefruit juice.

Prohibit concomitant use of strong CYP3A inducers ie, phenytoin, rifampin, enzalutamide, and St John's wort.

Prohibit use of CYP3A substrates with a narrow therapeutic index ie, alfentanil, cyclosporine, dihydroergotamine, ergotamine, everolimus, fentanyl, pimozide, quinidine, and tacrolimus).

(A frequently updated P450 drug interaction table is available at:  
<http://medicine.iupui.edu/clinpharm/ddis/>)

**Warning:** QTc prolongation can occur in patients treated with palbociclib and cetuximab. Avoid use of palbociclib with cetuximab in subjects with long QT syndrome. Avoid concomitant use of cetuximab and palbociclib that with agents known to prolong QTc interval or cause torsades de pointes (TdP).

A list of agents known to prolong QTc interval or cause torsades de pointes (TdP) can be found at: <https://www.crediblemeds.org>. A recently updated list as of July 22, 2017 is provided in Appendix 12.4.

**Agents with known risk for QTc prolongation or TdP are exclusionary.** Medications with possible risk (PR) or conditional risk (CR) of TdP should be used with caution and if an alternative agent is available, the alternative agent should be used instead. **Ondansetron at doses  $\leq 16$  mg or less is allowed.**

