#### **6.2.2 Adverse Events Associated With Cetuximab**

**Infusion reactions:** serious reactions, requiring medical intervention and immediate and permanent discontinuation of cetuximab included rapid onset of airway obstruction, hypotension, shock, loss of consciousness, myocardial infarction, and/or cardiac arrest. Approximately 90% of severe infusion reactions occurred with the first infusion despite premedication with antihistamines. See section 5.3.3 for management guidelines for infusion-related reactions.

**Cardiopulmonary arrest:** and/or sudden death occurred in 4 (2%) of 208 patients treated with radiation therapy and cetuximab.

**Pulmonary toxicity:** Interstitial lung disease, including 1 fatality, occurred in 4 of 1570 (<0.5%) patients receiving cetuximab in patients with CRC and head and neck cancer.

**Dermatologic toxicity:** including acneiform rash, skin drying and fissuring, paronychial inflammation, infectious sequelae (eg, aureus sepsis, abscess formation, cellulitis, blepharitis, conjunctivitis, etc.). See sections 5.3.2 for dose modification information. See sections 5.4.1 and Appendix 12.1 for skin toxicity prophylaxis and toxicity management guidelines.

Hypomagnesemia and electrolyte abnormalities: reported incidence in 55% of 365 patients receiving cetuximab for CRC and head and neck cancer, with 6-17% of patients experiencing grade 3 or grade 4 events.

Increased tumor progression, increased mortality or lack of benefit in patients with Ras-Mutant mCRC: Cetuximab is not indicated for use in patients with Ras-mutations of either K-ras, N-ras.

EGFR expression and response: in CRC patients response rate to cetuximab did not correlate with either the percentage of positive cells or the intensity of EGFR expression.

Patient Counseling Information:

Advise patients:

- To report signs and symptoms of infusion reactions such as fever, chills, or breathing problems
- Of the potential risks of using cetuximab during pregnancy or nursing and the need to use adequate contraception in both males and females during and for 6 months following the last dose of cetuximab
- That nursing is not recommended during, and for 2 months following the last dose of cetuximab
- To limit sun exposure (use sunscreen, wear hats) while receiving and for 2 months following the last dose of cetuximab

For additional details, please refer to the cetuximab package insert.

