## 12.0 APPENDICES

### 12.1 Management Guideline for Cetuximab Skin Toxicity

#### Management of Grade 2 Rash

Skin lesions and symptoms	Eruption with papules (grade 2A) or pustules (grade 2B) covering <50% of body surface, with moderate symptoms, and that does not interfere with daily activities
Cetuximab dose modifications	No
Topical treatment	Antibiotics: clindamycin 1% gel, erythromycin 3% gel/cream, metronidazole 0.75%-1% cream/gel, twice/day until regression to grade 1 (avoid benzoyl peroxide products). Lesions of the scalp: erythromycin 2% lotion
Systemic treatment	Prevalence of papules (grade 2A): No Prevalence of pustules (grade 2B): Antibiotics: minocycline 100 mg per os once/day, doxycycline 100 mg per os once/day for ≥4 weeks and until the rash is symptomatic

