#### Management of Grade 3 Rash

Skin lesions and symptoms	Eruption with papules (grade 3A) or pustules (grade 3B) covering >50% of body surface; severe symptoms that interfere with daily activities
Cetuximab dose modifications	First occurrence: delay cetuximab infusion for ≤21 days until the skin rash improves to grade ≤ 2. If there is an improvement, continue at 250 mg/m  . If there is no improvement, discontinue therapy. Second occurrence: delay cetuximab infusion for ≤21 days until the skin rash improves to grade ≤ 2. If there is an improvement, continue at reduced dose of 200 mg/m  . If there is no improvement, discontinue therapy. Third occurrence: delay cetuximab infusion for ≤21 days until the skin rash improves to grade ≤ 2. If there is improvement, continue at reduced dose of 150 mg/m  . If there is no improvement, discontinue therapy. Fourth occurrence: discontinue therapy definitively
Topical treatment	Antibiotics: clindamycin 1% gel, erythromycin 3% gel/cream, metronidazole 0.75-1% cream/gel, twice/day until regression to grade 1 (avoid benzoyl peroxide products). Lesions of the scalp: erythromycin 2% lotion
Systemic treatment	Antibiotics: minocycline 100 mg per os once/day, doxycycline 100 mg per os once/day for ≥4 weeks and until the rash is symptomatic Corticosteroids: methylprednisolone 0.4 mg/kg per os, prednisone 0.5 mg/kg per os, for up to 10 days
Systemic treatment in highly symptomatic/nonresponsive patients	Retinoids: isotretinoin 0.3-0.5 mg/kg per os Corticosteroids: methylprednisolone or dexamethasone i.v. Antihistamines: clorfenamine i.m./i.v. Antibiotics: amoxicillin/clavulanic acid, gentamicin i.v. Intravenous hydration

Reference: Carmine Pinto et al. The Oncologist 2011;16:228-238

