**Management of Grade 4 Rash**

Skin lesions and symptoms	Generalized rash; severe symptoms that require emergency treatment
Cetuximab dose modifications	Discontinue therapy immediately and definitively
Topical treatment	Antibiotics: clindamycin 1% gel, erythromycin 3% gel/cream, metronidazole 0.75%–1% cream/gel, 2 times daily until regression to grade 1 (avoid benzoyl peroxide products). Lesions of the scalp: erythromycin 2% lotion
Systemic treatment	Retinoids: isotretinoin 0.3–0.5 mg/kg per os Corticosteroids: methylprednisolone, dexamethasone i.v. Antihistamines: clorfenamine i.m./i.v. Antibiotics: amoxicillin/clavulanic acid, gentamicin i.v. Intravenous hydration Hospitalization

Reference: Carmine Pinto et al. The Oncologist 2011;16:228-238

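### Section 5.3.2 and Appendix 12.1 set different cetuximab delays and re-dosing criteria for severe (Grade 3) rash, and no text says which prevails

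*Combined protocol and SAP*

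**What the plan says.** Section 5.3.2 has a table for severe acneiform rash. At the first, second and third occurrence the instruction is "Delay infusion 1 to 2 weeks". If the rash improves, cetuximab continues at 250 mg/m2 the first time, drops to 200 the second and to 150 the third. If it does not improve, cetuximab stops. A fourth occurrence also stops it. The table gives no toxicity grade, either for the event or for the improvement.

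Appendix 12.1 has its own cetuximab dosing row in the Grade 3 rash table: "First occurrence: delay cetuximab infusion for ≤21 days until the skin rash improves to grade ≤ 2". The second and third occurrences carry the same delay and threshold. The dose steps are again 250, 200 and 150 mg/m2, with a stop at the fourth occurrence. After each delay the appendix adds: "If there is no improvement, discontinue therapy". Grade 4 rash has a separate rule: "Discontinue therapy immediately and definitively".

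Two cross-references bear on which text a site should follow. Section 6.2.2 says: "See sections 5.3.2 for dose modification information. See sections 5.4.1 and Appendix 12.1 for skin toxicity prophylaxis and toxicity management guidelines". The last line of Section 5.4.1, which begins "Management guidelines for skin toxicity (grade", points to Appendix 12.1 for Grade 2 or higher.

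**The concern.** Two operative texts appear to cover the same event with different instructions. At stake are patient safety and consistency between sites. For the same rash, one site could stop cetuximab permanently while another resumes it, or one could re-dose a patient who is still at Grade 3 while another holds. Section 6.2.2 lists infectious sequelae such as sepsis and abscess under cetuximab skin toxicity, so the re-dosing threshold matters clinically. The trial is multicenter, and Section 10.5 requires strict adherence to the protocol outside emergencies. Where the two rules diverge, it is unclear what counts as a deviation.

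**Working it through.** The plan states no figure to reproduce, so the check is a comparison of texts with a little arithmetic. Days are counted from the date on which the withheld infusion was due.

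**Do both rules cover the same event?** Section 5.3.2 says severe and gives no grade. Appendix 12.1 describes Grade 2 rash as "with moderate symptoms, and that does not interfere with daily activities" and Grade 3 rash as "severe symptoms that interfere with daily activities". The four-occurrence dose ladder is identical in both places. Equating severe with Grade 3 is therefore an inference, but the wording and the ladder both support it.

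**Where do they differ?**

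| Term | Section 5.3.2 | Appendix 12.1, Grade 3 |
|---|---|---|
| Minimum delay | 1 × 7 = 7 days | none |
| Maximum delay | 2 × 7 = 14 days | 21 days |
| Weekly infusions skipped at the maximum | 14 / 7 = 2 | 21 / 7 = 3 |
| Criterion for re-dosing | improvement, ungraded | Grade 2 or lower |
| Criterion not met | discontinue | discontinue |

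The maxima differ by 21 − 14 = 7 days, which is one infusion on the weekly schedule in Section 6.2.

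**What happens to a given rash?**

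- *Grade 2 or lower before day 7.* The appendix allows cetuximab to resume at once. Section 5.3.2 holds it until day 7.
- *Grade 2 or lower on days 7 to 14.* Both resume.
- *No improvement by day 14, then Grade 2 or lower on days 15 to 21.* Section 5.3.2 discontinues. The appendix, on its plain reading, resumes.
- *Improved but still Grade 3 at day 14, then Grade 2 or lower on days 15 to 21.* If any improvement counts, 5.3.2 re-doses at Grade 3, at the full 250 mg/m2 on a first occurrence, while the appendix holds and resumes later. If improvement means Grade 2 or lower, 5.3.2 discontinues and the appendix resumes.
- *Improved but still Grade 3 through day 21.* If any improvement counts, 5.3.2 re-doses and the appendix discontinues. If improvement means Grade 2 or lower, both discontinue.
- *No improvement through day 21.* Both discontinue.

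Reading the appendix threshold into 5.3.2 removes re-dosing at Grade 3. It does not remove the conflict over days 15 to 21, because the two time limits still differ.

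**The case against.** The best counter-argument is that the protocol already divides the roles. Section 6.2.2 names 5.3.2 for dose modification and, in the next sentence, the appendix for prophylaxis and toxicity management. The structure agrees: 5.3.2 sits under dose delays and modifications, the pointer to the appendix closes a supportive-care subsection, and the appendix's Grade 3 table carries a journal citation, so it looks like imported guidance. This has weight and suggests that 5.3.2 was meant to govern. It does not settle the matter, because the appendix contains a full dosing row, sites are sent to it for every rash of Grade 2 or higher, and no sentence subordinates it.

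A second argument is that 21 days is a ceiling. A site that waits 1 to 2 weeks, re-doses only at Grade 2 or lower and otherwise stops would stay within both texts. That course exists, but nothing tells sites to take it. The appendix on its face lets a patient recover on days 15 to 21 and continue, and 5.3.2 on its face allows re-dosing after any improvement.

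Three stronger readings are tempting and not supported:

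- *That the texts also conflict on Grade 4 rash.* They would only if severe in 5.3.2 were read to include Grade 4. The appendix gives Grade 4 its own explicit rule.
- *That the inconsistency disturbs the 4-month disease control rate or the Simon two-stage boundaries.* Nothing in the documents shows this.
- *That the appendix's 21 days is the correct limit.* No text prefers it to 14.

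**Conclusion.** The inconsistency is real and should be corrected. The two rules differ in minimum delay (7 days against none), maximum delay (14 against 21 days) and re-dosing criterion (ungraded against Grade 2 or lower). The clearest consequence is the late recovery with no improvement by day 14, which leads to permanent discontinuation under one text and continued cetuximab under the other, however improvement is defined. Re-dosing at Grade 3 is a further consequence only if any improvement suffices under 5.3.2.

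The conclusion assumes that severe in 5.3.2 means Grade 3, and that the appendix's 21 days is time a site may use. The documents give no rate of severe rash, so the number of patients affected is unknown. The dose ladder, the stop at a fourth occurrence and discontinuation when the criterion is not met all agree. This is a correction to treatment conduct, not to the statistical design.

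**What to change.** Keep a single cetuximab rash rule, in Section 5.3.2, that:

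- labels the table Grade 3, in line with the CTCAE grading used in 5.3.1 and 5.3.3;
- requires recovery to Grade 2 or lower before re-dosing;
- states one minimum delay, or that there is none;
- states one maximum delay, 14 or 21 days, chosen by the sponsor;
- discontinues cetuximab if Grade 2 or lower is not reached by that maximum;
- carries over the immediate and permanent stop for Grade 4.

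Replace the dosing row of the Grade 3 table in Appendix 12.1 with a reference to 5.3.2.

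The cost is a protocol wording amendment to one section and one appendix, with no change to sample size, visits or analysis. If the sponsor chooses 14 days, some patients will stop who could have continued under the appendix. Patients who have improved but are still at Grade 3 on day 14 will also stop, which 5.3.2 does not require now if any improvement suffices, so the amended text should say so openly.

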### 5.3.3 Management of infusion-related reactions

Approximately 90% of severe infusion reactions occur with the first infusion of cetuximab. Monitor patients for 1 hour following cetuximab infusions in a setting with resuscitation equipment and other agents necessary to treat anaphylaxis.

Monitor longer to confirm resolution of the event in patients requiring treatment for infusion-related reactions.

NCI CTCAE Grade	Treatment	Premedication at subsequent dosing
Grade 1 Mild reaction; infusion interruption not indicated; intervention not indicated	Increase monitoring of vital signs as medically indicated until the subject is deemed medically stable in the opinion of the investigator.	None
Grade 2 Requires infusion interruption but responds promptly to symptomatic treatment (e.g., antihistamines, NSAIDS, narcotics, IV fluids); prophylactic medications indicated for $\leq$ 24 hrs	
Stop Infusion and monitor symptoms. Additional appropriate medical therapy may include but is not limited to:
 
 
• IV fluids,
 
• antihistamines,
 
• NSAIDS,
 
• acetaminophen,
 
• narcotics.
 
 
Increase monitoring of vital signs as medically indicated until the subject is deemed medically stable in the opinion of the investigator.
 
If symptoms resolve within one hour of stopping drug infusion, the infusion may be restarted at 50% of the original infusion rate (e.g., from 100 mL/hr to 50 mL/hr). Otherwise dosing will be held until symptoms resolve and the subject should be pre-medicated for the next scheduled dose.
	
Subject may be pre-medicated 1.5h (<math>\pm</math> 30 minutes) prior to infusion of cetuximab with:
 
Diphenhydramine 50 mg po (or equivalent dose of antihistamine).
 
Acetaminophen 500-1000 mg po (or equivalent dose of antipyretic).

Continued on next page


Grades 3 or 4
 
Grade 3: Prolonged (i.e., not rapidly responsive to symptomatic medication and/or brief interruption of infusion); recurrence of symptoms following initial improvement; hospitalization indicated for other clinical sequelae (e.g., renal impairment, pulmonary infiltrates)
 
Grade 4: Life-threatening; pressor or ventilatory support indicated
	
Stop Infusion. Additional appropriate medical therapy may include but is not limited to:
 
 
• IV fluids,
 
• antihistamines,
 
• NSAIDS,
 
• acetaminophen,
 
• narcotics,
 
• oxygen,
 
• pressors,
 
• corticosteroids,
 
• epinephrine
 
 
Increase monitoring of vital signs as medically indicated until the subject is deemed medically stable in the opinion of the investigator. Hospitalization may be indicated.
 
Subject is permanently discontinued from further trial treatment administration.
	
No subsequent dosing

Appropriate resuscitation equipment should be available in the room and a physician readily available during the period of drug administration.
		

## 5.4 Concomitant Medications/Treatments/Supportive Care Allowed

Patients on the trial are allowed to receive all supportive care therapy needed to alleviate symptoms related to CRC or other medical problems at the investigator's discretion (see prohibited medications in section 5.5 for exceptions). No treatments should be withheld due to a patient's participation in this study. Prophylaxis for infusion-related reactions should be employed per institutional guidelines. A guidance for the management of infusion-related reactions is provided in section 5.3.3 of the protocol. (Note: Ondansetron at doses  $\leq$  16 mg or less is allowed).

### 5.4.1 Management of Cetuximab Skin Toxicity

Before initiating cetuximab treatment, the following prophylactic measures should be discussed with the patient to help alleviate the risk for skin toxicity.

- Using sunscreens
- Avoiding habits/products that can produce dry skin (eg, hot water, alcohol-based cosmetics)
- Enhancing skin hydration (bath oils, etc.)
- Using frequently alcohol-free moisturizing creams
- Using tocopherol oil or gel
- Avoiding tight shoes and
- Avoiding excessive beard growth, shaving with regular shaving razor, sharp multiblade, using pre-shaving cream emollients and moisturizing aftershave, not using alcohol and aftershave or using electric shaver.
- Prophylaxis against skin eruption with minocycline or doxycycline may be used per institutional guidelines.

**Management guidelines for skin toxicity (grade  $\geq 2$ ) are provided in Appendix 12.1**

### **5.5 Prohibited Medications/Treatments**

There are no reported drug-drug interactions with cetuximab. However, palbociclib, is primarily metabolized by CYP3A and sulfotransferase enzyme (SULT2A1). In vivo, palbociclib is a time-dependent inhibitor of CYP3A. The patient handout in Appendix 12.2 should be provided to patients to inform them of drugs to avoid taking while they are receiving study medications.

Prohibit use of strong CYP3A inhibitors ie, clarithromycin, indinavir, itraconazole, ketoconazole, lopinavir/ritonavir, nefazodone, nelfinavir, posaconazole, ritonavir, saquinavir, telaprevir, telithromycin, and voriconazole. Avoid grapefruits and grapefruit juice.

Prohibit concomitant use of strong CYP3A inducers ie, phenytoin, rifampin, enzalutamide, and St John's wort.

Prohibit use of CYP3A substrates with a narrow therapeutic index ie, alfentanil, cyclosporine, dihydroergotamine, ergotamine, everolimus, fentanyl, pimozide, quinidine, and tacrolimus).

(A frequently updated P450 drug interaction table is available at:  
<http://medicine.iupui.edu/clinpharm/ddis/>)

**Warning:** QTc prolongation can occur in patients treated with palbociclib and cetuximab. Avoid use of palbociclib with cetuximab in subjects with long QT syndrome. Avoid concomitant use of cetuximab and palbociclib that with agents known to prolong QTc interval or cause torsades de pointes (TdP).

A list of agents known to prolong QTc interval or cause torsades de pointes (TdP) can be found at: <https://www.crediblemeds.org>. A recently updated list as of July 22, 2017 is provided in Appendix 12.4.

**Agents with known risk for QTc prolongation or TdP are exclusionary.** Medications with possible risk (PR) or conditional risk (CR) of TdP should be used with caution and if an alternative agent is available, the alternative agent should be used instead. **Ondansetron at doses  $\leq 16$  mg or less is allowed.**

### **5.6 Duration of Therapy**

Treatment may continue until:

- Disease progression
- Inter-current illness that prevents further administration of treatment

- Unacceptable adverse event(s)
- Pregnancy
- Patient decides to withdraw from study treatment, **OR**
- General or specific changes in the patient's condition render the patient unacceptable for further treatment in the judgment of the investigator.
- Subject completes maximum number of treatment cycles allowed per protocol
- Subject is lost to follow up

It is anticipated that subjects will receive on average 4 to 6 months of study treatment.

### **5.7 Duration of Follow Up**

All patients will be followed for up to 3 years, or until death, whichever occurs first after removal from study treatment for determination of study endpoints. Patients removed from study treatment for unacceptable AEs will be followed for resolution or stabilization of the adverse event(s). All patients (including those withdrawn for AEs) should be followed after removal from study treatment as stipulated in the protocol.

### **5.8 Study Withdrawal**

Patients will be removed from protocol therapy and the PI notified when any of the criteria listed in section 5.6 apply. The reason for discontinuation of protocol therapy will be documented on the eCRF.

If a patient decides to withdraw from the study (and not just from protocol therapy) an effort should be made to complete and report study assessments as thoroughly as possible. At the time of withdrawal, the investigator should attempt to establish as completely as possible the reason for the study withdrawal.

- The patient should be asked if they are willing to allow for the abstraction of relevant information from their medical record in order to meet the long term follow up (e.g., survival) objectives outlined in the protocol.
- A complete final evaluation at the time of the patient's study withdrawal should be obtained with an explanation of why the patient is withdrawing from the study.
- If the patient is noncompliant and does not return for an end of study follow up assessment, this should be documented in the eCRF.
- If the reason for removal of a patient from the study is an adverse event, the principal specific event will be recorded on the eCRF.

Excessive patient withdrawals from protocol therapy or from the study can render the study un-interpretable; therefore, unnecessary withdrawal of patients should be avoided.

